8.2.2 Definition of Variables

8.2.2.1 Recurrence-free survival is the time from enrollment to disease recurrence or the last follow-up (censored). Recurrence is defined by suspicious lesion noted by tumor imaging according to RECIST 1.1. Tissue proof for suspicious lesion is recommended if it is feasible.

8.2.2.2 Overall survival is the time from enrollment to death of any cause or the last follow-up (censored).

8.2.2.3 Evaluation of Toxicity: The incidence and severity of toxicity will be summarized according to the NCI Common Toxicity Criteria Version 4.0.

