Duration of Participation	
Subjects need to sign the informed consent form to be enrolled into this trial.After a screening phase up to 28 days, each subject will receive adjuvant weekly cisplatin -CRT (cisplatin, 30mg/m²/week x 2; radiotherapy, 180-200 cGy/fraction x 10-13) followed by pembrolizumab (200mg/3 weeks x 18) (approx. a total of 56 weeks).Treatment will continue until the completion of the planned cisplatin-CRT plus 18 cycles of pembrolizumab, or until recurrent disease, unacceptable adverse events, intercurrent illness that prevents further administration of treatment, investigator's decision to withdraw the subject, subject withdrawal of consent, pregnancy of the subject, noncompliance with trial treatment, or administrative reasons requiring cessation of treatment.To detect the tumor recurrence, all patients will be evaluated by pertinent evaluation and imaging studies every 4 cycles of pembrolizumab during treatment phase, then every 3 months for post-treatment year-1 to year-2, and every 6 months for post-treatment year-3 and year-4.Subjects who discontinue for reasons other than recurrent disease will have post-treatment follow-up visits for monitoring disease status as if they were still on treatment until recurrent disease, initiating a non-study cancer treatment, withdrawing consent from study participation, or becoming lost to follow-up.All subjects will be followed (e.g., by telephone or visit) for overall survival until death, withdrawal of consent from study participation, or the end of the study, whichever comes first. After the end of study treatment, each subject will be followed for 30 days for adverse event monitoring. Serious adverse events will be

	collected for 90 days after the end of treatment or for 30 days after the end of treatment if the subject initiates new anticancer therapy, whichever is earlier.
Estimated average length of treatment per patient	56 weeks

[figure not shown]

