Overall, these observations in ESCC are in line with those in head and neck squamous cell carcinoma (HNSCC), a disease which shares very similar risk factors with ESCC. The close/involved resection margin and ENI have been recognized as the most significant prognostic factors for HNSCC. Hence, HNSCC patients with these poor prognostic factors are now routinely treated with postoperative CRT [21,22].

Based on the afore-mentioned data, the local guidelines at our center thus recommend adjuvant CRT for locoregional esophageal cancer patients who have either close/involved margin or ENI of involved lymph nodes following preoperative CRT plus surgery. Nevertheless, our recent analysis indicated that despite of adjuvant CRT, the prognosis of these patients with high risk of recurrence, i.e., involved margin, positive LN with ENI, and ypN2-3, remains very poor. Their median recurrence-free survival (RFS) was 6.7 months and their 1-year RFS rate was 32.3% (subgroup analysis for [12]).

Immune checkpoint blockade holds promise as a promising therapy for ESCC

Recently, blockade of immune checkpoints, including cytotoxic T lymphocyte antigen 4 (CTLA-4) and PD-1/PD-L1, has demonstrated promising clinical activities in multiple cancer types. The clinical activity against multiple cancer types have been generally moderate, with objective tumor response rates in the range of 15~ 30%. Mutational load and neoantigen have been identified as one of the potential biomarkers for immune checkpoints blockade [23,24]. With the advance of sequencing techniques, large-scale genomic sequencing in increasing number of patients has been conducted in multiple cancer types, including ESCC. The mutational load of ESCC is more than median in many cancer types [25–29].

The expression of PD-L1/PD-L2, another one potential biomarker for PD-1/PD-L1 blockade, was found in 42% and 48%, respectively of ESCC tumors [30]. Intratumoral abundance of CD4 and CD8 T cells has also been reported as a prognostic factor in ESCC patients [31]. The preliminary anti-tumor activity of PD-1/PD-L1 immune checkpoint blockers as a single agent in advanced esophageal cancer patients who have progressed on standard systemic chemotherapy has been recently reported. The objective tumor response of pembrolizumab in ESCC patients with positive PD-L1 expression was 29% [32]. Another study using another anti-PD-1 monoclonal antibody in a group of ESCC patients (N = 65) reported a response rate of 16% [33].

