8.2 Statistical Analysis Plan

8.2.1 Sample Size Determination

According to the subgroup analysis of our previous study [12], the median RFS for locally advanced ESCC patients who have received preoperative cisplatin-based CRT followed by surgery, and exhibit high risk of tumor recurrence (defined as closed or involved margin [$\leq 1\text{mm}$] or ENI or ypN2-3) is 6.7 months, equivalent to a 1-year RFS rate of 32.3%. It would need a sample size of 24 patients to detect a difference of the 1-year RFS rate from 32% to 60% by calculated using an exact binomial test with a power of 80% and a 5% significance level. Having taken an additional 10% of early drop-out rate into consideration, the total enrolled patient number will be 26 for this study. We estimate an enrollment rate of 12 patients per year at my center. Therefore, total study period will be 5 years, including 2 years of patient enrollment and 3 years of patient follow-up.

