8.2.3 General Statistical Consideration

8.2.3.1 All statistical analyses will be performed for intent-to-treatment population.

8.2.3.2 The survival estimates will be derived from Kaplan and Meier curves.

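### The RFS definition counts only documented recurrence as an event, so deaths without recurrence are censored and the primary 1-year RFS rate is overstated whenever such deaths occur

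*Combined protocol and SAP*

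**What the plan says.** Section 4.2.4.1 makes the 1-year RFS rate the primary endpoint. The only working definition of RFS is in Section 8.2.2.1: "Recurrence-free survival is the time from enrollment to disease recurrence or the last follow-up (censored". The same item limits what counts as recurrence: "Recurrence is defined by suspicious lesion noted by tumor imaging according to RECIST 1.1". Tissue confirmation is recommended where feasible but not required. Tumor imaging covers esophagoscopy as well as CT (Section 6.1, footnote e; Section 7.1.5.2).

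The next item, Section 8.2.2.2, treats death differently: "Overall survival is the time from enrollment to death of any cause or the last follow-up (censored".

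Section 8.2.3 sets the population and the estimator: "All statistical analyses will be performed for intent-to-treatment population" and "The survival estimates will be derived from Kaplan and Meier curves". Section 8.2.1 sizes the trial for a rise from 32% to 60% at one year, "calculated using an exact binomial test with a power of 80% and a 5% significance level". The 32% comes from the centre's earlier series, described in Section 4.2.1: "Their median recurrence-free survival (RFS) was 6.7 months and their 1-year RFS rate was 32.3% (subgroup analysis for [12".

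Sections 2.1, 4.2.1, 4.2.4.1, 8.1 and 8.2.1 all use RFS without listing its events. Section 7.1.5.5 mentions death only as a point at which collection of disease status ends. No section makes death an RFS failure.

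**The concern.** Read as written, the definition has one event and one censoring rule. A patient who dies without a documented lesion has not met the event, so is censored at last follow-up. Under Kaplan-Meier that patient is treated as someone who could still have recurred later, at the same rate as those remaining at risk. The curve then estimates net time to recurrence, not survival free of recurrence.

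This matters because it is the primary endpoint of a 26-patient single-arm trial, where one or two reclassified patients visibly move the result. A fatal toxicity or another non-cancer death in the first year would not count against the treatment in the primary analysis. Nor would a death between scheduled scans (every 4 cycles, about 12 weeks on treatment) before recurrence was documented. These deaths are not hidden: they count in overall survival and, within the reporting window, as serious adverse events. They just do not register where the main efficacy claim is made.

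A second consequence is conditional. If the historical 32.3% counted deaths as failures, the trial would compare a recurrence-only rate with a recurrence-or-death rate, and its false-positive rate would rise.

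**Working it through.** **Inputs from the documents.** Historical rate 32%, target 60%, 24 patients, exact binomial test, 80% power (Section 8.2.1); two-sided 5% (Section 2.1); 26 enrolled.

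**Assumed input.** d, the proportion of patients who die without documented recurrence within one year. The documents give no figure, so 0%, 5%, 10% and 15% are used.

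**1. The plan's own figure.** With 24 patients and p = 0.32, the smallest cut-off with upper tail at most 0.025 is 13: P(X ≥ 13) = 0.0202. Power at 0.60 is 0.787, close to the stated 80%. The plan states no cut-off; 13 of 24 is derived here.

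**2. Direction.** At each event Kaplan-Meier multiplies by (1 − 1/number at risk). Censoring a death instead of counting it removes a factor below 1 and leaves later risk sets unchanged. The estimate can only stay the same or rise.

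**3. Size under constant hazards.** Let S be the true 1-year probability of being alive and recurrence-free. The share of the total hazard due to death without recurrence is f = d/(1 − S). With those deaths censored, Kaplan-Meier estimates S^(1 − f).

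| d | f at S = 0.60 | estimate | f at S = 0.32 | estimate |
|---|---|---|---|---|
| 0% | 0 | 60.0% | 0 | 32.0% |
| 5% | 0.125 | 64.0% | 0.074 | 34.8% |
| 10% | 0.250 | 68.2% | 0.147 | 37.8% |
| 15% | 0.375 | 72.7% | 0.221 | 41.1% |

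**4. Size by direct count, with no hazard assumption.** Take 26 patients all followed for one year, 16 alive and recurrence-free (16/26 = 61.5%) and 10 failures. Suppose m of the 10 are deaths without recurrence and are censored. If those deaths come before all the recurrences, the estimate is 16/(26 − m); if they come after, it is (16 + m)/26. Other orderings fall between.

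- m = 1: 16/25 = 64.0% to 17/26 = 65.4%
- m = 2: 16/24 = 66.7% to 18/26 = 69.2%
- m = 3: 16/23 = 69.6% to 19/26 = 73.1%

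**5. False-positive rate, only if the 32% benchmark counted deaths.** The true recurrence-or-death-free rate is set at 32% with n = 24, and the trial is called positive at 13/24 or above. The plan does not say how Kaplan-Meier estimation and the binomial test fit together, so three readings are shown. The first is simulated (400,000 runs per set); the others are exact binomial tails.

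| Reading | d = 0% | 5% | 10% | 15% |
|---|---|---|---|---|
| Kaplan-Meier estimate as defined, compared with 13/24 | 2.0% | about 3.2% | about 6.4% | about 11.8% |
| Count of patients, early deaths classed as recurrence-free (p = 0.32 + d) | 2.0% | 6.5% | 15.8% | 30.8% |
| Count of patients, early deaths classed as failures (p = 0.32) | 2.0% | 2.0% | 2.0% | 2.0% |

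**The case against.** Five points can be made for the plan.

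- **Silence is not a rule.** Section 8.2.2.1 never says deaths are censored, and the word survival in the endpoint's name suggests death was meant to count. But then the name and the definition conflict, and an analyst programs the definition. The contrast with the overall survival item makes the literal reading hard to dismiss, and nothing elsewhere corrects it.
- **The benchmark may use the same rule.** The 32.3% comes from the same centre under the same label. If it also censored deaths, the comparison is like for like and the false-positive rate does not rise. This stands. It does not rescue the reported rate as a measure of patients alive and recurrence-free, and the documents do not allow the match to be checked.
- **The size is assumed.** True: no document supports any value of d. Entry requires ECOG 0-1 and recovery from surgery, which should exclude some early postoperative deaths. One such death among 26 moves the estimate by 2.5 to 3.9 points, against a binomial standard error of √(0.6 × 0.4/26) = 9.6 points. But this is a systematic shift in one direction, and Section 4.2.2 itself describes these patients as frail.
- **The false-positive figures depend on an unstated decision rule.** This stands too; they are illustrations. The spread from 2.0% to 30.8% shows how much is left open by not saying how an early death is classed.
- **A recurrence endpoint fits the hypothesis.** Section 3.1 does speak of reducing recurrence. That supports reporting time to recurrence as well, but the stated primary objective is RFS.

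**Conclusion.** The concern holds. As written, documented recurrence is the only RFS event, and the Kaplan-Meier 1-year rate exceeds the proportion alive and recurrence-free whenever someone dies in the first year without documented recurrence. The wording and the direction of the effect are certain; the size is not. At a true rate near 60%, each such death among 26 patients adds roughly 2.5 to 4 points, and d of 5% to 15% adds about 4 to 13 points under constant hazards. With no such deaths the bias is zero. Inflation of the false-positive rate is a further possibility that arises only if the 32.3% benchmark counted deaths. Because this is the event definition of the primary endpoint, it must be corrected before analysis.

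**What to change.** 1. Rewrite Section 8.2.2.1 so that RFS runs from enrollment to the first documented recurrence or death from any cause, whichever comes first. Patients alive and recurrence-free are censored at their last disease assessment. Make clear that a death counts even if the patient had already moved to telephone survival follow-up after starting another cancer treatment.
2. State in Section 8.2.1 or 8.2.3 that a death before 12 months is a failure in any binomial test of 1-year RFS.
3. Confirm from the centre's own data that the 32.3% uses the same event definition. If it does not, restate the historical rate and recheck the sample size of 24 (26 with drop-out).
4. If time to recurrence is of interest, report it as a secondary measure by cumulative incidence, with death as a competing event.

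The cost is a short SAP amendment and one look back at the historical series. No new trial data are needed, since Section 1.0 already provides: "All subjects will be followed (e.g., by telephone or visit) for overall survival until death". The downside is that the reported 1-year RFS may be lower, by the gaps shown in the working.

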4.2.4 Rationale for Endpoints

4.2.4.1 Efficacy Endpoints

1. The primary endpoint is the 1-year RFS rate.
2. The secondary endpoints include median RFS, 3-year OS rate, median OS time, 3-year RFS rate, safety and toxicity.

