5.8 Subject Withdrawal/Discontinuation Criteria

Subjects may withdraw consent at any time for any reason or be dropped from the trial at the discretion of the investigator should any untoward effect occur. In addition, a subject may be withdrawn by the investigator or the Sponsor if enrollment into the trial is inappropriate, the trial plan is violated, or for administrative and/or other safety reasons. Specific details regarding discontinuation or withdrawal are provided in Section 7.1.4 – Other Procedures.

A subject must be discontinued from the trial for any of the following reasons:

- The subject or legal representative (such as a parent or legal guardian) withdraws consent.
- Confirmed radiographic disease recurrence
- Unacceptable adverse experiences as described in Section 5.2.1.2
- Intercurrent illness that prevents further administration of treatment
- Investigator's decision to withdraw the subject
- The subject has a confirmed positive serum pregnancy test
- Noncompliance with trial treatment or procedure requirements
- The subject is lost to follow-up
- Administrative reasons

The End of Treatment and Follow-up visit procedures are listed in Section 6 (Protocol Flow Chart) and Section 7.1.5 (Visit Requirements). After the end of treatment, each subject will be followed for 30 days for adverse event monitoring (serious adverse events will be collected for 90 days after the end of treatment as described in Section 7.2.3.1). Subjects who discontinue for reasons other than recurrent disease will have post-treatment follow-up for disease status until disease recurrence, initiating a non-study cancer treatment, withdrawing consent or becoming lost to follow-up. After documented disease recurrence each subject will be followed by telephone for overall survival until death, withdrawal of consent, or the end of the study, whichever occurs first.

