7.1.5.5.1 Survival Follow-up

Once a subject experiences confirmed disease recurrence or starts a new anti-cancer therapy, the subject moves into the survival follow-up phase and should be contacted by telephone

every 12 weeks to assess for survival status until death, withdrawal of consent, or the end of the study, whichever occurs first.

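### The primary RFS event is a suspicious lesion on imaging with no rule for a lesion later disproved, while stopping and follow-up act on an undefined 'confirmed' recurrence

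*Combined protocol and SAP*

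**What the plan says.** Section 4.2.4.1 states: "The primary endpoint is the 1-year RFS rate". Section 8.2.2.1 measures recurrence-free survival from enrollment to recurrence, and defines the event: "Recurrence is defined by suspicious lesion noted by tumor imaging according to RECIST 1.1". The next sentence adds: "Tissue proof for suspicious lesion is recommended if it is feasible". A footnote to the flow chart in section 6.1 likewise asks for tissue only where feasible. No section says what happens to the event, or to its date, when tissue or a later scan shows no recurrence.

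The operational sections use other words:

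- Section 5.8 lists as a reason for discontinuation "Confirmed radiographic disease recurrence".
- Section 7.1.5.5.1, with the same wording in footnote b of section 6.1, says: "Once a subject experiences confirmed disease recurrence or starts a new anti-cancer therapy, the subject moves into the survival follow-up phase".
- Section 5.8 also says: "After documented disease recurrence each subject will be followed by telephone for overall survival".
- The Trial Summary (section 1.0) has treatment continue to completion "or until recurrent disease, unacceptable adverse events" or another listed reason, with no qualifier on recurrence.

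Neither confirmed nor documented recurrence is defined.

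**The concern.** The endpoint is triggered by suspicion, while discontinuation and the move to telephone follow-up are mostly triggered by confirmation. Consider a patient with a suspicious lesion at an on-treatment scan and a negative biopsy. Under a literal reading of 8.2.2.1 that patient has had the primary event. Under 5.8 and 7.1.5.5.1 the patient has not recurred and stays under disease follow-up.

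The documents make such patients plausible. Pembrolizumab follows radiotherapy to the esophageal and mediastinal region (5.2.2). Section 5.6.1 asks investigators to rule out other causes, including metastatic disease, when they assess immune-related disorders.

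With 26 patients, one miscounted patient moves a simple 1-year proportion by 1/26 = 3.8 percentage points. The error lowers observed RFS, so it works against the regimen.

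**Working it through.** **Inputs.** Null 32%, target 60%, exact binomial test, 80% power, 5% level, 24 patients needed and 26 enrolled (8.2.1). The 5% is two-sided (2.1). The historical 1-year RFS is 32.3% (4.2.1, 8.1).

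**The plan's own figure.** The pass mark r is the smallest count of relapse-free patients with P(X ≥ r | n, 0.32) ≤ 0.025. Power is P(X ≥ r | n, 0.60).

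- n = 24: r = 13, upper-tail error 0.0202, power 78.7%.
- n = 26: r = 14, upper-tail error 0.0172, power 80.1%.

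The stated design reproduces closely. The plan gives no pass mark; 14 of 26 is derived here.

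**A fixed number miscounted (assumed).** If k patients truly free at 1 year are scored as relapsed, at least r + k truly free patients are needed to pass. Power is then P(X ≥ r + k | n, 0.60).

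| k | n = 26, r = 14 | n = 24, r = 13 |
|---|---|---|
| 0 | 80.1% | 78.7% |
| 1 | 67.4% | 65.0% |
| 2 | 52.1% | 48.9% |

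With a one-sided 5% level and n = 26, the pass mark would be 13 and the sequence 89.2%, 80.1%, 67.4%.

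**A miscounted share (assumed).** If a share f of truly free patients is miscounted, the observed rate is 0.60 × (1 − f). For n = 26 and r = 14:

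- f = 2%: rate 0.588, power 76.3%.
- f = 5%: rate 0.570, power 70.1%.
- f = 10%: rate 0.540, power 58.6%.

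If the true rate were 32%, f = 5% would give an observed rate of 0.304, and the upper-tail error would drop from 0.0172 to 0.0107. The test becomes conservative and false success is not inflated.

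**The benchmark condition.** All these losses take 32% and 60% as rates under stricter scoring. If both were set under the same imaging rule, the observed rate at the target is already 0.60, power stays at 80.1% and the loss is zero. The documents do not settle this. Section 4.2.1 says the historical high-risk patients had adjuvant CRT, so radiotherapy changes may already be in the 32.3%. Changes due to pembrolizumab, which this trial adds (3.1), would not be.

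**Dates.** On-treatment imaging is every 4 cycles of 3 weeks, so 4 × 3 = 12 weeks apart. If confirmation means the next scheduled scan, the suspicious and confirmed dates differ by about 12 weeks and can fall on either side of 12 months.

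**The case against.** The strongest reply is that 8.2.2.1 never says a disproved lesion remains an event. It recommends tissue proof, presumably so that the result can inform the call. That is fair: counting such a lesion follows from a literal reading and is not a stated outcome. Even so, the sentence does define recurrence by the suspicious lesion, and nothing in the plan reverses it.

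A reader might infer that the plan holds two competing RFS definitions, to be chosen between after the data are seen. It does not. Section 8.2.2.1 is the only definition of RFS. The other sections govern discontinuation and follow-up, their wording is mixed, and confirmed radiographic recurrence need not mean tissue-proven.

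A reader might also infer that the wording certainly costs power. The documents give no false-positive rate, the counts of 1 and 2 are assumptions, and the loss vanishes if the benchmark and target share the imaging rule.

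Two further cautions stand. Section 8.2.3.2 says survival estimates come from Kaplan-Meier curves, so the binomial pass mark is a model of the primary test and not a stated decision rule. Also, 8.2.2.1 does not list death as an RFS event. That separate matter pushes RFS upward, so the net bias of the endpoint is not settled here.

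**Conclusion.** The point holds as a defect of definition. The primary event rests on suspicion, there is no route to remove a disproved lesion, and the rest of the protocol uses undefined and inconsistent terms for recurrence. Read literally, a patient with a biopsy-negative lesion, or one that resolves without new anticancer therapy, counts as relapsed.

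The effect is conditional. With 26 patients, a pass mark of 14 and a true rate of 60%, 1 or 2 miscounted patients would take power from 80.1% to about 67% or 52%. This assumes that those patients are otherwise free at 1 year and that the 32% benchmark was not scored the same way. If either fails, the loss is smaller or absent. The documents do not support a claim that such a loss is expected, only that the plan leaves it possible and that wording can prevent it.

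**What to change.** In 8.2.2.1:

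1. Keep the first scan showing the lesion as the event date.
2. State that a lesion disproved by biopsy, or resolved on later scheduled imaging without new anticancer therapy, is not an RFS event.
3. State that an unresolved suspicious lesion followed by new anticancer therapy or death is an event at the lesion date.

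State how recurrence was scored for the historical 32.3%. Report the primary result under the literal imaging rule as a sensitivity analysis. This also covers a lesion that resolves while pembrolizumab continues, where a benign change and a treated recurrence cannot be told apart without tissue.

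The recurrence wording in 1.0, 5.8, 6.1, 7.1.5.5.1 and 8.2.2.1 must be reconciled. No treatment-stopping rule is proposed.

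The cost is protocol and SAP wording, with no added patients, scans or biopsies. Some event calls will be settled only at the next scheduled scan. A benign change that persists and is never sampled would still count as an event.
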